1.5 Rationale and Study Design

We hypothesize more complete blockade of the ER-signaling pathway may be achieved with selective estrogen receptor downregulator fulvestrant (given at a high dose) than may be achieved with the steroidal AI exemestane, and that this will result in either comparable or greater effectiveness for the fulvestrant-everolimus combination than the exemestane-everolimus combination. This is supported by preclinical data demonstrating that fulvestrant is particularly effective when combined with agents targeting the PI3K-AKT-m-TOR pathway in tumors that have undergone long-term estrogen deprivation, as is the case for patients who have acquired resistance to AI therapy.⁵⁰

We therefore propose to study the efficacy of fulvestrant in combination with everolimus for the treatment of post-menopausal HR-positive metastatic breast cancer in women who have progressed after treatment with an aromatase inhibitor. The combination of a novel class of agents (mTOR inhibitors) and an established standard treatment for metastatic HR-positive breast cancer may potentially increase the clinical benefit by targeting multiple different biological pathways.

This is a randomized, double-blind, placebo controlled Phase II study. It is expected that 130 patients will be accrued at 25 centers within the US. Patients will be randomized (1:1) to receive everolimus or placebo after consideration of stratification factors of performance status (0 vs.1), measurable disease (with or without non-measurable) vs. non-measurable disease, and prior chemotherapy for metastatic disease vs. no prior chemotherapy.

Induction Phase:

Treatment during the Induction Phase includes:

Fulvestrant 500 mg IM (two-250 mg injections per dose) on day 1 & 15 of Cycle 1, then 500 mg IM (two-250 mg injections) on day 1 of all subsequent cycles (every 28 days) plus everolimus 10 mg (two- 5 mg tablets) PO daily

OR

Fulvestrant 500 mg IM (two-250 mg injections per dose) on day 1 & 15 of Cycle 1, then 500 mg IM (two-250 mg injections) on day 1 of all subsequent cycles (every 28 days) plus placebo two tablets PO daily

Patients will be evaluated for disease response every 12 weeks (every 3 treatment cycles), +/- 1 week, and treated until disease progression, unacceptable toxicity or for a total of up to 12 cycles.

Continuation Phase:

Patients with no evidence of progressive disease who remain on study after completing Cycle 12 will be unblinded and proceed to the Continuation Phase. Patients in the Continuation Phase should continue to receive fulvestrant alone (if originally randomized to placebo) **or** in combination with everolimus (if originally randomized to everolimus) at the same dose and schedule. Patients will continue to be evaluated for disease response every 12 weeks (every 3 treatment cycles), +/- 1 week, and may continue treatment until disease progression or unacceptable toxicity.

All patients will be followed for 30 days for toxicity after the last dose of study therapy (fulvestrant and/or everolimus/placebo) or until recovery from all toxicity (to \leq grade 1) attributed to study therapy, whichever is longer (or if $>$ grade 1, event must be permanent and stable).

2 Objectives

2.1 Primary Objective

To assess progression-free survival in post-menopausal patients with hormone-receptor positive metastatic breast cancer that is resistant to aromatase inhibitor therapy treated with fulvestrant and everolimus compared to fulvestrant alone.

2.2 Secondary Objectives

To describe the safety profile, objective response rate, time to progression and overall survival in this patient population.

3 Selection of Patients

3.1 Eligibility Criteria

Each of the criteria in the following section must be met in order for a patient to be considered eligible for this study.

PrECOG will not grant any exceptions or waivers to protocol eligibility criteria.

In calculating pre-treatment days of tests and measurements, the day a test or measurement is done is considered Day 0. Therefore, if a test is done on a Monday, the Monday four weeks later would be considered Day 28.

Note: All questions regarding eligibility should be directed to the PrECOG Study Contact in study materials. Questions will be further discussed with the medical leads for the trial as deemed appropriate (e.g., medical monitor, study chair).

Investigator sites may use the eligibility checklist (see Appendix A: Eligibility Checklist) which will be provided as a separate study document, as documentation that eligibility criteria were verified. If used, it should be reviewed, signed, and dated prior to patient randomization by the treating physician, and all required elements of source documentation must be found in the patient record (e.g. scans, consent, pathology).

Inclusion Criteria:

1. Must be willing to sign a protocol-specific informed consent.
2. Patients must be 18 years of age or older.
3. Patients must have an ECOG Performance Status 0 or 1 (see Appendix B: ECOG Performance Status Scale).
4. Patients must have histologically or cytologically confirmed adenocarcinoma of the breast.
5. Patients must have stage IV disease or inoperable locally advanced disease.
6. Patients must have ER and/or PR-positive disease as determined by their local pathology or reference laboratory by ASCO-CAP criteria.⁵¹ Tumors must be HER-2/neu negative or equivocal by standard ICH/FISH or ICH/CISH methodologies by ASCO-CAP criteria.⁵²
7. Patients must be Aromatase Inhibitor (AI) resistant, defined as:
 - relapsed while receiving adjuvant therapy with an aromatase inhibitor (anastrozole, letrozole, or exemestane) or,
 - progressive disease while receiving an aromatase inhibitor for metastatic disease.

Note: Patients may have received an endocrine agent (e.g., Tamoxifen) between the time of progression on an AI and registration.

8. Patients who have received one prior cycle (dose on day 1 and day 15) of fulvestrant within 28 days of randomization are eligible so long as they meet other eligibility criteria.
 - patients previously treated with two or more prior cycles of fulvestrant are not eligible.
9. Patients must be female and postmenopausal, defined as:
 - a history of at least 12 months without spontaneous menstrual bleeding or,
 - prior bilateral salpingo-oophorectomy, with or without hysterectomy or,
 - age \geq 55 years with a prior hysterectomy with or without oophorectomy or,
 - age <55 years with a prior hysterectomy without oophorectomy or unknown status, with a documented FSH level in postmenopausal range within 4 weeks of randomization or,
 - receiving a gonadotropin releasing hormone analog (GnRH) to suppress ovarian function (e.g., goserelin 3.6 mg q 4 weeks).
10. Patients may have received up to one prior systemic chemotherapy regimen for metastatic disease.
11. Adequate organ function, as evidenced by ALL the following obtained within 4 weeks of randomization*:
 - total white blood cell count (leukocytes, WBC) $\geq 3.0 \times 10^9/L$, absolute neutrophil count (ANC) $\geq 1.5 \times 10^9/L$ and platelet count $\geq 100 \times 10^9/L$
 - hemoglobin $\geq 9 \text{ g/dL}$
 - serum bilirubin $\leq 1.5 \times \text{ULN}$
 - AST or ALT $\leq 2.5 \times \text{ULN}$ ($\leq 5 \times \text{ULN}$ in patients with liver metastases)
 - serum creatinine $\leq 1.5 \times \text{ULN}$
 - serum albumin $\geq 3 \text{ g/dL}$
 - fasting serum cholesterol $\leq 300 \text{ mg/dL}$ OR $\leq 7.75 \text{ mmol/L}$ **AND** fasting triglycerides $\leq 2.5 \times \text{ULN}$. **Note:** In case one or both of these thresholds are exceeded, the patient can only be included after initiation of appropriate lipid lowering medication.
 - PT with INR ≤ 1.5 (Anticoagulation is allowed if target INR ≤ 1.5 on a stable dose of warfarin or on a stable dose of LMW heparin for >2 weeks at time of randomization.)

*Please see study table in Section 7.0 for labs that may need to be repeated within ≤ 7 days of Cycle 1 Day 1 (C1D1).

12. Patients may have measurable disease, non-measurable disease (e.g., bone only metastases), or both per RECIST Version 1.1 Criteria. Measurable lesions are defined as those that can be accurately measured in at least one dimension (longest diameter to be recorded) as $\geq 20 \text{ mm}$ by chest x-ray, as $\geq 10 \text{ mm}$ with CT scan, or $\geq 10 \text{ mm}$ with calipers by clinical exam. All tumor measurements must be recorded in millimeters (or decimal fractions of centimeters). **Note:** Tumor lesions that are situated in a previously irradiated area are not considered measurable.

13. Patients with basal cell or squamous cell carcinoma of the skin or carcinoma *in situ* of the cervix within the past five years must have been treated with curative intent. Patients with a history of prior malignancy are eligible provided they were treated with curative intent and have been free of disease for >3 years.

Exclusion Criteria:

1. Patients who have had any major surgery or significant traumatic injury within 4 weeks of randomization, or have not recovered from the side effects of any major surgery (defined as requiring general anesthesia) or patients that may require major surgery during the course of the study are not eligible. (Placement of vascular access device will not be considered major surgery.)
2. Patients may not be receiving any other investigational agents or have received any investigational agent within 4 weeks of randomization.
3. Patients must not be receiving any concomitant anticancer treatment or have received anticancer treatment within 4 weeks of randomization (including chemotherapy, radiation therapy, antibody based therapy, etc.), with the following exceptions:
 - Bisphosphonates, Zometa or Xgeva for bone metastases
 - Hormonal therapy (e.g., AI, Tamoxifen)
 - a GnRH analog is permitted if the patient had progressive disease on a GnRH analog plus a SERM or an AI; the GnRH analog may continue but the SERM or AI must be discontinued.
4. Patients must not have received prior treatment with an mTOR inhibitor (sirolimus, temsirolimus, everolimus).
5. Patients must not be receiving chronic, systemic treatment with corticosteroids or another immunosuppressive agent greater than or equal to 5 mg prednisone or its equivalent daily. Topical or inhaled corticosteroids are allowed.
6. Patients must not receive immunization with attenuated live vaccines within one week of randomization or during the study period. Close contact with those who have received attenuated live vaccines should be avoided during treatment with everolimus. Examples of live vaccines include intranasal influenza, measles, mumps, rubella, oral polio, BCG, yellow fever, varicella and TY21a typhoid vaccines.
7. Patients must not have current or a prior history of brain metastases or leptomeningeal disease. Patients must not have rapidly progressive, life-threatening metastases. This includes patients with extensive hepatic involvement (>50% of the liver involved) and symptomatic lymphangitic metastases.
8. Patients must not have a known hypersensitivity/history of allergic reactions attributed to compounds of similar chemical or biologic composition to everolimus (or other rapamycins such as sirolimus, temsirolimus) or fulvestrant.

9. Since everolimus may cause bone marrow suppression, patients with congenital or acquired immune deficiency at increased risk of infection are not eligible. This includes patients being treated with chronic immunosuppressive agents (including greater than or equal to 5 mg prednisone or its equivalent daily), and patients with known HIV seropositivity.
10. Patients must not have any impairment of gastrointestinal function or gastrointestinal disease that may significantly alter the absorption of everolimus (e.g., ulcerative disease, uncontrolled nausea, vomiting, diarrhea, malabsorption syndrome or small bowel resection).
11. Patients must not have an active, bleeding diathesis.
12. Patients must not have a history of any condition or uncontrolled intercurrent illness including, but not limited to, ongoing or active infection or psychiatric illness/social situations that in the opinion of the local investigator might interfere with or limit the patient's ability to comply with the protocol or pose additional or unacceptable risk to the patient.
13. Patients must not have any severe and/or uncontrolled medical conditions or other conditions that could affect their participation in the study such as:
 - Symptomatic congestive heart failure of New York Heart Association Class III or IV (see Appendix D)
 - Unstable angina pectoris, myocardial infarction within 6 months of randomization, serious uncontrolled cardiac arrhythmia or any other clinically significant cardiac disease
 - History of symptomatic pulmonary disease or non-malignant pulmonary disease (e.g. COPD) requiring treatment. Such patients would be eligible if PFTs performed within 8 weeks of treatment noted a DLCO greater than 50%.
 - Uncontrolled diabetes as defined by fasting serum glucose $>1.5 \times \text{ULN}$
(Note: Optimal glycemic control should be achieved before starting trial therapy.)
 - Active (acute or chronic) or uncontrolled severe infections
 - Liver disease such as cirrhosis or severe hepatic impairment (Child-Pugh Class C).

Note: A detailed assessment of Hepatitis B/C medical history and risk factors must be done at screening for all patients. HBV DNA and HCV RNA PCR testing are required at screening for all patients with a positive medical history based on risk factors and/or confirmation of prior HBV/HCV infection. (see Section 7.1.1 for additional details).

4 Randomization Procedures

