Patients must have ER and/or PR-positive disease as determined by their local pathology or reference laboratory by ASCO-CAP criteria. ⁵¹ Tumors must be HER-2/neu negative or equivocal by standard ICH/FISH or ICH/CISH methodologies by ASCO-CAP criteria. ⁵²  ER+  PR+  ER+ and PR+  Tumor is HER-2/neu negative by standard ICH/FISH or ICH/CISH methodologies Pathology Date: ____ / ____ / ____  Pathology must be in patient record		
Patients must have had relapse while receiving adjuvant therapy with an aromatase inhibitor (anastrozole, letrozole, or exemestane), OR progressive disease while receiving an aromatase inhibitor for metastatic disease. Note: Patients may have received an endocrine agent (e.g., Tamoxifen) between the time of progression on an AI and registration.  Documentation in patient record		
Patients previously treated with two or more prior cycles of fulvestrant are not eligible. Patients who have received one prior cycle (dose on day 1 and day 15) of fulvestrant within 28 days of randomization are eligible as long as they meet other eligibility criteria.  Documentation in patient record		
Patients must be post menopausal. (see Section 3.1)  Documentation in patient record		

	Pt Initials: _____ F M L	Study Personnel: _____ Date of Evaluation: ____/____/_____

Patient may have received up to one prior systemic chemotherapy regimen for metastatic disease.
 
 no prior systemic chemotherapy
 
 one prior systemic chemotherapy regimen
 
 documentation in patient record
		

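### Inclusion 9: from a year after hysterectomy, the no-bleeding limb admits women under 55 with ovaries retained or unknown without the FSH that the fourth limb requires

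*Protocol*

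**What the plan says.** Section 3.1 of the protocol, Inclusion 9, opens with "Patients must be female and postmenopausal, defined as" and then gives five limbs. Each of the first four ends in 'or'.

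- Limb 1: "a history of at least 12 months without spontaneous menstrual bleeding or".
- Limb 2: "prior bilateral salpingo-oophorectomy, with or without hysterectomy or".
- Limb 3: age at or above "55 years with a prior hysterectomy with or without oophorectomy or".
- Limb 4: "age <55 years with a prior hysterectomy without oophorectomy or unknown status, with a documented FSH level in postmenopausal range", the FSH to be obtained in the 4 weeks before randomization.
- Limb 5: "receiving a gonadotropin releasing hormone analog (GnRH) to suppress ovarian function".

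No text ranks the limbs or confines limb 1 to women who still have a uterus. The checklist in Appendix A says "Patients must be post menopausal" and points back to Section 3.1. The synopsis and SAP Section 4.2 use the word postmenopausal without defining it. The primary objective (Section 2.1) begins "To assess progression-free survival in post-menopausal patients with hormone-receptor positive metastatic breast cancer". Protocol Section 9 and SAP Section 7.2 restrict the primary efficacy analysis to patients who are both eligible and treated.

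**The concern.** Limbs 3 and 4 show that the plan does not accept absence of periods as proof of menopause in a woman under 55 without a uterus: it asks for an FSH unless her ovaries are out or suppressed. Limb 1 gives the same woman a route that skips the FSH, so one stated rule defeats another.

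Two things are at stake. First, women whose ovarian function nobody has verified can enter a trial whose objective concerns postmenopausal patients. Second, eligibility decides who is in the primary analysis. A woman under 55, several years after hysterectomy, with her ovaries and no FSH result, is eligible if limb 1 is taken literally. She is ineligible if limb 4 is taken to govern women after hysterectomy. With 25 centers and no waivers of eligibility criteria, sites could call the same case differently.

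**Working it through.** The plan gives no figure to reproduce here; the check is one of logic.

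**Inputs.** The five limbs of Inclusion 9 and their 'or' connectors, and Exclusion 1, which rules out major surgery in the 4 weeks before randomization. I assume that hysterectomy counts as major surgery.

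**Set-up.** Take a woman under 55 who has had a hysterectomy, whose ovaries remain or are of unknown status, and who is not on a GnRH analog. Let *t* be the months since hysterectomy and *b* the months since her last menstrual bleed. She cannot menstruate after the operation, so *b* ≥ *t*. Limb 1 is met when *b* ≥ 12. Limb 2 is not documented, limb 3 fails on age and limb 5 does not apply. Only limbs 1 and 4 can admit her.

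**Cases.**

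1. *t* ≥ 12. Then *b* ≥ *t* ≥ 12, so limb 1 is met. She qualifies whatever her FSH, and limb 4 has no effect.
2. *t* between 4 weeks and 12 months, *b* ≥ 12. Her periods had stopped early enough before surgery, so limb 1 is met and limb 4 has no effect.
3. *t* between 4 weeks and 12 months, *b* < 12. Limb 1 fails and the FSH in limb 4 decides.
4. *t* under 4 weeks. Exclusion 1 removes her.

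**Result.** The FSH test decides eligibility only in case 3. That window is at most 52 − 4 = 48 weeks, about 11 months, after surgery.

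**Limb 3.** A woman aged 55 or over with *t* ≥ 12 meets limb 1 as well as limb 3, and a woman under 55 with *t* ≥ 12 meets limb 1 by case 1. From a year after hysterectomy, being above or below 55 therefore makes no difference, although limbs 3 and 4 were written to make it matter.

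**The case against.** The best reply is that nobody would read limb 1 this way. A question about menstrual bleeding is naturally put to a woman who can menstruate, and applying limb 1 after hysterectomy empties limbs 3 and 4 of most of their content. That is probably the intended reading. It does not settle the matter, because the text does not say so and sites apply the text.

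There are partial safeguards. Inclusion 7 requires relapse or progression while on an aromatase inhibitor, and Section 1.3 describes these drugs as the preferred choice in postmenopausal women. Many entrants will thus already have been judged postmenopausal or ovarian-suppressed. Eligibility questions go to the study contact, and the site confirms eligibility at randomization. These steps reduce the exposure, but the last two only check the patient against the same criteria. The SAP's sensitivity analysis of all randomized patients also limits the damage from inconsistent classification, though the primary analysis stays exposed.

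A reader might infer that the missing FSH line in Section 7 and Section 7.1.1 is a further defect. It is not: limb 4 orders the test and sets its window, and Section 7.1.1 requires whatever assessments eligibility needs.

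It can also be said that confining limb 1 simply to women with an intact uterus would demand an FSH from a woman under 55 whose periods stopped a full year before a later hysterectomy. She properly meets limb 1 now. That objection stands, and the fix below allows for it.

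**Conclusion.** The point holds as a conflict between stated rules. From 12 months after hysterectomy, limb 1 admits a woman under 55 with ovaries retained or of unknown status without the FSH that limb 4 requires, and limb 3's age split is redundant likewise. This rests only on reading the limbs as alternatives, which is how they are written.

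The size cannot be given. The documents report no distribution of age, hysterectomy or time since surgery for this population. Three stronger readings are tempting and are not supported:

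- That the FSH check hardly ever applies. The documents show only that it cannot decide eligibility beyond the first year; they do not show how many women fall inside or outside that year.
- That the trial loses power. Any estimate needs an assumed number of such women, an assumed share with functioning ovaries, and an assumed loss of everolimus effect in them. The documents supply none of these.
- That the comparison is biased. The criterion rests on facts fixed before randomization, so it does not favor either arm.

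The effect on the PFS comparison is probably small. What remains is a looser population than the objective describes, and room for inconsistent eligibility calls in the primary analysis set.

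**What to change.** Reconcile limbs 1, 3 and 4 so that limb 1 does not override the hysterectomy limbs. One way is to state that limb 1 counts only months without bleeding while the uterus was in place: either the uterus is intact, or the 12 months were completed before hysterectomy. All other women after hysterectomy would be assessed under limbs 2 to 5. The Appendix A checklist refers back to Section 3.1 and would follow automatically.

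The sponsor should also say where a woman under 55 with a hysterectomy and only one ovary removed belongs. Limb 1 may admit her now, and after the change no limb would clearly name her.

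The cost is a phrase in Inclusion 9. A few women would need the FSH test that limb 4 already specifies, and some of them may fail screening.

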4.1 Ethics

This study will be conducted in accordance with the ethical principles that have their origin in the current Declaration of Helsinki and will be consistent with applicable US regulatory requirements and International Conference on Harmonization Good Clinical Practice (ICH GCP).

The study will be conducted in compliance with the protocol. The protocol and any amendments and the patient informed consent will receive Institutional Review Board (IRB) approval prior to initiation of the study.

Freely given written informed consent must be obtained from every patient or their legally acceptable representative prior to clinical trial participation, including informed consent for any screening procedures conducted to establish patient eligibility for the trial.

Study personnel involved in conducting this trial will be qualified by education, training, and experience to perform their respective task(s). This trial will not use the services of investigators or study personnel where sanctions have been invoked or where there has been scientific misconduct or fraud (e.g., loss of medical licensure, debarment). Investigators are responsible for the conduct of the study at their study site.

4.2 Regulatory Requirements

Before a site may enter patients, protocol-specific regulatory and other documents must be submitted to PrECOG as noted in study materials. Detailed information regarding document submission and control is provided to each site in separate study materials.

Once all required documents are received, reviewed and approved by PrECOG or their representative, a Study Reference Manual (SRM) will be forwarded to the site. Any changes to site regulatory documents must be submitted by the investigator to the responsible party in a timely manner. Initial study drug shipment will not occur until the regulatory packet is complete. No patients will begin protocol therapy without formal randomization as per the process below.

